For patients who require dual chamber pacing, patients will be randomized to His bundle versus left bundle area pacing for active fixation. We will evaluate the acute and follow-up capture threshold of His bundle versus left bundle pacing.

Objectives

Primary Objective

To compare 3 month follow up complete ventricular capture thresholds of His bundle pacing versus left bundle area pacing lead placement. Complete loss of capture will be measured with a width of 1.0 ms and during unipolar or bipolar output, whichever value is lower.

Secondary Objectives

To compare changes in left ventricular performance and mechanical synchrony, selective or non selective-His Pacing, left bundle area pacing, in patients who require ventricular pacing at 3 months.

The endpoints collected will be:

1. Ejection Fraction
2. Stroke volume
3. Mechanical dyssynchrony, characterized by the time to peak systolic velocity of the Left Ventricle (LV) myocardial walls, elicited by tissue Doppler:
 - a. Anterior
 - b. Posterior
 - c. Anterior-Septal
 - d. Anterior-Lateral
 - e. Lateral
 - f. Inferior-lateral
4. QRS duration

Other secondary endpoints collected will be:

1. 6 month complete loss of capture threshold as defined in the primary endpoint.
2. 12 month complete loss of capture threshold as defined in the primary endpoint

Methods

Design

Single center, open label, randomized pilot study to evaluate the complete ventricular capture thresholds of His Bundle versus left bundle area pacing.

Secondary analysis will focus on echocardiographic hemodynamic parameters of HIS pacing, versus left bundle branch pacing.

Based on previous studies ([Vijayaraman, Naperkowski, et al., 2018](#)) and our experience with non-selective and left bundle area pacing, a difference of 0.5 V at 1.0 ms in capture threshold at 3 month follow-up between His and left bundle area pacing sites, is to be expected. With a standard deviation of 0.5 V, This would require an enrollment of 20 patients to obtain a power of 0.8 to demonstrate

statistical significance. Thus we anticipate enrollment of 26 patients to evaluate differences in capture threshold between the studied pacing sites, and an expected 20% patient drop out.

Enrollment

Investigators providing care will be tasked with patient screening. This will be performed at both the inpatient and outpatient arenas, and can occur within any timeframe prior to the pacemaker implant. During the screening process, patients will be given consent forms to be reviewed collectively with an investigator.

Statistical Analysis

Continuous variables will be reported as mean +/- standard deviation. Categorical variables will be expressed as percentages. Paired comparisons will be made using a Student t-test if the data is normally distributed, and with the Wilcoxon signed-rank test for nonparametric data. Paired categorical data will be compared using the Wilcoxon test. P-value ≤ 0.05 was considered significant.

Randomization

Randomization will be in a 1:1 assignment. Twenty-six envelopes with random assignments to one of the two treatment arms will be created. As patients are enrolled, they will be assigned to an envelope. Each envelope number will be correlated with patient information, as well as date of procedure, and assigned ID number.

Randomization will occur after the patient demonstrates acceptable selective or non-selective HIS bundle pacing prior to active fixation.

If the patient is identified at the Beaumont Troy site, the above shall still continue to apply. The key personnel will bring the randomization card to the site on the day of the procedure.

Study Population

Inclusion Criteria

Prospective enrollment of patients:

1. Over 18 years old
2. Signed consent
3. Pacemaker indication according to 2018 ACC/ AHA HRS Guideline on the Evaluation and Management of Patients with Bradycardia and Cardiac Conduction Delay with one or more of the following
 - a. Symptomatic sinus node dysfunction.
 - b. Symptomatic Atrioventricular (AV) block or high degree AV block.
 - c. Tachy-Brady syndrome

Exclusion Criteria

Patients with any condition of the following will be excluded:

1. Previously implanted cardiac pacing devices except transvenous temporary pacemaker.
2. Patients who are eligible for appropriate cardiac resynchronization therapy(CRT) or implantable cardiovert defibrillator (ICD) implantation
3. Patients with prior septal myectomy
4. Patients with prior surgical or transcatheter aortic valve replacement
5. Anatomy precluding implant evaluated during the screening or identified during the procedure.
6. Those without ability to achieve selective His bundle pacing evaluated during the screening or identified during the procedure
7. Pregnant women

Pre-Operative Characterization

After enrollment, patients will be evaluated in the Heart Rhythm Center Holding Center, prior to pacemaker implant.

A baseline 12 lead EKG will be obtained prior to or at the onset of the procedure, and the following will be collected.

1. QRS duration
2. QRS morphology

Patients will then be randomized, after the selective or non-selective HIS bundle pacing can be achieved, to either selective His bundle, or left bundle pacing site for active fixation of the ventricular lead.

The following baseline characteristics will be collected:

1. Age
2. Sex

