3. QRS
4. Known Coronary artery Disease
5. Previous Atrial Fibrillation
6. Hypertension
7. Diabetes
8. Peripheral Vascular Disease
9. Renal Failure
10. Systolic blood pressure
11. Diastolic blood pressure
12. Pulse pressure
13. New York Heart Association (NYHA) class
14. Left ventricular Ejection fraction (LVEF)

15. Pacing indications
16. Etiology of cardiomyopathy (if applicable)

Procedural Protocol

Patients will be prepped and draped in the usual sterile fashion. The 12 lead surface electrodes will be covered with sterile towels. Incision and subcutaneous pocket in the deltopectoral region will be created using standard technique.

Venous accesses are to be obtained by axillary vein or cephalic cut-down access utilizing modified Seldinger technique. Sheaths are to be placed into the venous system.

His Bundle Pacing is now included in the ACC/AHA guidelines for pacemaker implants. For those operators who chose to implant a pacemaker lead at the His bundle, the Medtronic 3830 lead is the standard of care. The region just distal to the His bundle is now being recognized as the Left bundle area pacing. Given both the His bundle and the right ventricle pacing, including the left bundle area, are standard of care with the 3830Medtronic Lead, there is no increased risk to the device use in this study. Additionally, the Medtronic 3830 lead has been FDA approved since July 12, 2018 for implantation of His bundle pacing and has an excellent safety and performance record.

For the ventricular lead placement, it is to be performed using the Select Secure (3830, 69 cm, Medtronic Inc.) pacing lead delivered through a fixed-curve (C315 HIS, Medtronic Inc.) or a deflectable catheter delivery system (Attain, Medtronic Inc.). The sheath is to be advanced, over the wire to the right ventricle. The 3830 leads will be inserted through the selected sheath and the tip of lead will be exposed from the sheath. The lead will be connected to the electrophysiological recording system on the atrial channel, with gain setting of 0.05 mV/mm, and a sweep speed of 50 mm/sec.

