A standard of care echo done within 3 months of the procedure will be used as the baseline echo. Data acquired from the echo will be and assessed by a single, non-blinded Cardiac Echocardiographer. Tissue doppler if not performed during the echo, post processing will be utilized if possible.

To evaluate the hemodynamic properties of the pacing site, echocardiography will be utilized.

Hemodynamic assessment will be obtained by collecting stroke volume at each site, utilizing the velocity time integral. The VTI will be obtained in the apical long axis view.

Left ventricular ejection fraction will also be assessed at each pacing site utilizing the biplane method of disks.

Tissue Doppler imaging will be used to assess longitudinal LV dyssynchrony. Myocardial velocity curves are to be obtained from the apical 2 and 3 chamber views. These views are selected to assess the anterior, inferior, lateral anterior-septal, inferior-septal, and inferior lateral left ventricular walls. The peak sustained myocardial systolic velocity (during the ejection phase) for each of the 4-LV segments is to be identified. The time to peak systolic velocity will be measured with reference to the onset of QRS complex.

The following data will be collected:

1. Left ventricular Ejection Fraction
2. Stroke volume (by VTI)
3. The peak sustained myocardial systolic velocity (during the ejection phase) for each of the 4-LV segments is to be identified:
 - a. Anterior
 - b. Anterior-Septal
 - c. Inferior-Septal
 - d. Inferior
 - e. Inferior-lateral
 - f. Lateral

Electrocardiographic evaluation

During the procedure, a 12-lead electrocardiogram will be available, and recorded while atrio-ventricular paced. The following will be collected:

1. The stimulation-to-QRS
2. QRS duration
3. QRS morphology
4. Pacing stimulus to left ventricular activation time (LVAT) in unipolar lateral precordial leads V4-V6

The following will be collected after active fixation, during the most narrow QRS morphology obtained:

1. The stimulation-to-QRS
2. QRS duration
3. QRS morphology
4. Pacing stimulus to left ventricular activation time (LVAT) in unipolar lateral precordial leads V4-V6

Procedural Data

Data collected will be:

1. Fluoroscopic time
2. Amount of contrast administered
3. Procedural time

Device Evaluation

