3. Complete loss of capture
4. Impedance values at the site of active fixation will be collected
5. Sensed R wave amplitudes

Follow-up

Patients will be assessed in the outpatient area at 3 (\pm 1 month), and 6 months (\pm 1 month), and 12-month (\pm 1 month) post implant. A 12-lead electrocardiogram will be obtained while the patient is set to a parameter that ensures selective His ventricular pacing or the narrowest QRS achievable with left bundle area pacing, depending on the randomization group.

1. The following will be collected at 3 months during pacing which yields the most narrow QRS, at 1.0 ms pulse duration: The stimulation-to-QRS
2. QRS duration
3. QRS morphology
4. Pacing stimulus to left ventricular activation time (LVAT) in unipolar lateral precordial leads V4-V6
5. Pacing burden

The device will be interrogated to obtain the following at 3month

Unipolar

1. Selective Capture
2. Non-selective
3. Complete loss of capture
4. Impedance values at the site of active fixation will be collected
5. Sensed R wave amplitudes

Bipolar

1. Selective Capture
2. Non-selective
3. Complete loss of capture
4. Impedance values at the site of active fixation will be collected
5. Sensed R wave amplitudes

The device will be interrogated to obtain the following at 6 months during pacing which yields the most narrow QRS, at 1.0 ms pulse duration::

1. stimulation-to-QRS
2. QRS duration
3. QRS morphology
4. Pacing stimulus to left ventricular activation time (LVAT) in unipolar lateral precordial leads V4-V6
5. Pacing burden

Unipolar

1. Selective Capture
2. Non-selective
3. Complete loss of capture
4. Impedance values at the site of active fixation will be collected
5. Sensed R wave amplitudes

Bipolar

1. Selective Capture
2. Non-selective
3. Complete loss of capture
4. Impedance values at the site of active fixation will be collected
5. Sensed R wave amplitudes

The following will be collected at 12 months, during pacing which yields the most narrow QRS, at 1.0 ms pulse duration:

1. The stimulation-to-QRS
2. QRS duration
3. QRS morphology
4. Pacing stimulus to left ventricular activation time (LVAT) in unipolar lateral precordial leads V4-V6
5. Pacing burden

The device will be interrogated to obtain the following at 12 months:

Unipolar

1. Selective Capture
2. Non-selective
3. Complete loss of capture
4. Impedance values at the site of active fixation will be collected
5. Sensed R wave amplitudes

Bipolar

1. Selective Capture
2. Non-selective

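### The secondary objective compares changes between randomised arms, but only paired tests are named and the collected baselines enter no between-arm analysis

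*Combined protocol and SAP*

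**What the plan says.** The Secondary Objectives section sets out "To compare changes in left ventricular performance and mechanical synchrony" at 3 months. The endpoints are ejection fraction, stroke volume, time to peak systolic velocity by left ventricular wall, and QRS duration. That sentence lists the pacing sites without stating a contrast. The Design section supplies it: the secondary analysis sets His pacing against left bundle pacing.

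On allocation, the Randomization section says "Randomization will be in a 1:1 assignment". Each patient has the ventricular lead fixed at one site.

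On method, the Statistical Analysis section says "Paired comparisons will be made using a Student t-test if the data is normally distributed". It gives the Wilcoxon signed-rank test for nonparametric data and a Wilcoxon test for paired categorical data. It names no independent-groups test, between-arm change score or baseline-adjusted model.

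Baselines are collected:
- QRS: "A baseline 12 lead EKG will be obtained prior to or at the onset of the procedure" (Pre-Operative Characterization).
- LVEF: listed among the baseline characteristics.
- Echo: "A standard of care echo done within 3 months of the procedure will be used as the baseline echo" (Echocardiographic Evaluation Protocol).
- Tissue Doppler, with less certainty: "Tissue doppler if not performed during the echo, post processing will be utilized if possible".

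The Follow-up section collects ECG data, device data and an echocardiogram at 3 months.

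**The concern.** A paired test on baseline and 3-month values asks whether one group changed over time. It does not estimate how far the His arm differs from the left bundle arm, which is what the objective asks. Followed literally, the plan yields two within-arm p-values per endpoint and no arm difference. The risk is that significance in one arm only is read as evidence that the sites differ.

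A second issue arises once a between-arm comparison is named. The baselines could make it more precise if they correlate with the 3-month values, and the plan does not say whether or how they would be used. With about 20 evaluable patients, that choice has a visible effect on power.

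**Working it through.** **Inputs from the documents.** Allocation is 1:1. The sample-size paragraph gives 20 patients needed, 26 enrolled and 20% dropout (26 × 0.8 = 20.8), so about 10 evaluable per arm. The significance level is 0.05; sidedness is not stated and two-sided is assumed. That sample size belongs to the primary threshold endpoint. The plan has no power figure for the secondary endpoints, so there is none to reproduce.

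**Assumed, because the documents give no values.** Equal SDs at baseline and 3 months; baseline-to-follow-up correlation r of 0.3, 0.5 and 0.7, with 0 as the worst case; effects in SD units.

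**Step 1: paired tests within each arm, same true change in both.** The SD of the change is SD × √(2(1−r)). For a 0.5-SD change and n = 10, the noncentrality is √10 × 0.5/√(2(1−r)) = 1.34, 1.58 and 2.04 on 9 df. Power per arm is p = 0.223, 0.293 and 0.446. The chance that exactly one arm is significant is 2p(1−p) = 0.347, 0.414 and 0.494. It depends on the assumed change:

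| Common true change | r = 0.3 | r = 0.5 | r = 0.7 |
|---|---|---|---|
| none | 10% | 10% | 10% |
| 0.2 SD | 14% | 16% | 20% |
| 0.5 SD | 35% | 41% | 49% |
| 1 SD | 45% | 32% | 9% |

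**Step 2: variance of the arm difference, relative to comparing 3-month values alone.** Change score: 2(1−r). ANCOVA: (1−r²)(N−3)/(N−4) with N = 20, that is (1−r²) × 17/16; the factor 17/16 allows for chance baseline imbalance.

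| r | Change score | ANCOVA | ANCOVA ÷ change score |
|---|---|---|---|
| 0 | 2.00 | 1.062 | 0.531 |
| 0.3 | 1.40 | 0.967 | 0.691 |
| 0.5 | 1.00 | 0.797 | 0.797 |
| 0.7 | 0.60 | 0.542 | 0.903 |

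ANCOVA breaks even with 3-month-only where (1−r²) × 17/16 = 1, so |r| = √(1/17) = 0.243. The change score has the smaller variance only where (1+r)/2 × 17/16 > 1, that is r above 15/17 = 0.88.

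**Step 3: power, from the noncentral t** (ANCOVA on 17 df, averaged over chance baseline imbalance).

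| Effect | r | 3-month only | Change score | ANCOVA |
|---|---|---|---|---|
| 1 SD | 0 | 56% | 32% | 54% |
| 1 SD | 0.3 | 56% | 43% | 58% |
| 1 SD | 0.5 | 56% | 56% | 66% |
| 1 SD | 0.7 | 56% | 78% | 82% |
| 0.5 SD | 0.3 | 19% | 15% | 19% |
| 0.5 SD | 0.5 | 19% | 19% | 22% |
| 0.5 SD | 0.7 | 19% | 28% | 30% |

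**Step 4: missing baselines.** Assume 5 of 20 are missing at random and the effect is 1 SD. In 40,000 simulations, ANCOVA with the missing baseline set to the pooled mean has power 57%, 62% and 72% at r = 0.3, 0.5 and 0.7. Complete-case ANCOVA has 43%, 50% and 66%. The 3-month-only comparison, which needs no baseline, has 56%. Rejection under the null was 4.8% to 5.1% for all methods.

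**The case against.** The strongest reply is that the defect is simply a missing independent-groups test, which also affects the primary threshold comparison. On that view ANCOVA is only a preference among valid methods, for secondary endpoints in a pilot. The section says how paired comparisons will be made; it does not say that they are run arm by arm or that nothing else will be done. Part of this stands. An unpaired comparison of 3-month values or of changes would be valid under randomisation, and the primary endpoint shares the gap. But the signed-rank test is specifically a paired or one-sample test, so the text cannot be read as naming an unpaired one, and any repair has to name a method.

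Other points that stand:
- The one-arm-only rate depends on the assumed change, from about 9% to 50% over the values tried.
- The gain from ANCOVA is small at low correlation. At r = 0.3 with 5 baselines missing it has 57% power against 56% for 3-month-only. Complete-case ANCOVA falls below no adjustment at r = 0.3 and 0.5.
- QRS may gain least. The baseline is pre-implant, while the follow-up value is taken under pacing ("The following will be collected at 3 months during pacing which yields the most narrow QRS, at 1.0 ms pulse duration"). Its correlation could fall below the 0.24 break-even.
- Replacing the paired tests with ANCOVA alone would drop the plan's nonparametric route, and wall-by-wall models add multiplicity.

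These limit the size of the benefit. They do not supply a between-arm analysis where the plan has none.

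**Conclusion.** The concern holds. The tests named cannot answer the secondary objective, and this does not depend on any assumed number. How often two within-arm tests would mislead, and how much a baseline covariate would help, rest on assumed correlations, SDs and effects with 10 evaluable per arm. For r from 0.3 to 0.7, ANCOVA cuts variance by 31% to 10% against a change score and by 3% to 46% against 3-month values alone. At r = 0 it costs about 6% against the latter. For a 0.5-SD difference every method is weak, at 15% to 30% power, so estimates with confidence intervals matter more than tests. The plan should be changed on this point; because the endpoints are secondary, it does not undermine the trial as a whole.

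**What to change.** Add to the Statistical Analysis section wording such as:

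> 3-month LVEF, stroke volume and QRS duration will each be compared between randomised arms by ANCOVA with the pre-implant value of the same measure as covariate. The adjusted mean difference and 95% CI will be reported, with the unadjusted 3-month difference alongside. Patients with a 3-month value but no baseline stay in the analysis, with the missing baseline set to the mean of all observed baselines, both arms pooled.

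To go with it:
- Keep a nonparametric route, but as an independent-groups rank test in place of the signed-rank test.
- Apply the same model to time to peak systolic velocity, wall by wall, where a matching baseline exists, and label these results exploratory. First reconcile the wall lists: only anterior, anterior-septal, lateral and inferior-lateral appear both under Secondary Objectives and in the echo data lists. Those data lists also name peak velocity, whereas the endpoint is time to peak.
- Word the baseline echo as done within 3 months before implant.

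The cost is wording, one degree of freedom per model and a missing-baseline rule. LVEF and QRS need no new data; stroke volume and tissue Doppler depend on what the standard-of-care echo allows. The precision loss is at most about 6% of variance, and arises only if the correlation is below about 0.24.

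### The echo objective can be read as choosing patients by pacing need after randomisation, and no section defines the echo analysis set

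*Combined protocol and SAP*

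**What the plan says.** The Secondary Objectives compare changes in left ventricular performance and mechanical synchrony for His pacing and "left bundle area pacing, in patients who require ventricular pacing at 3 months". The endpoints listed there are ejection fraction (EF), stroke volume, tissue Doppler time to peak systolic velocity, and QRS duration.

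Entry is described differently. The opening statement reads "For patients who require dual chamber pacing, patients will be randomized to His bundle versus left bundle area pacing for active fixation". Inclusion criterion 3 asks for a guideline pacemaker indication "with one or more of the following": "Symptomatic sinus node dysfunction", AV block, or "Tachy-Brady syndrome". Any one is enough, so AV block is not required.

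"Pacing indications" are listed as a baseline characteristic under Pre-Operative Characterization. "Pacing burden" is collected at 3, 6 and 12 months under Follow-up. The Statistical Analysis section uses neither. It names paired tests only, and it gives no between-arm model and no analysis set for the echo endpoints.

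Under Follow-up, the 3-month echo and ECG are recorded with the device set so that the patient is paced from the assigned site, whatever the day-to-day burden.

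**The concern.** If the phrase on pacing need defines who is analysed, membership is settled at 3 months, after the lead has been placed. Randomisation does not protect a comparison within a group formed that way. If site or programming influences who is counted as needing pacing, the arms of the subset are no longer comparable. No burden cut-off or other rule for membership is given. The trial is open label, and the Echocardiographic Evaluation Protocol has the echo data read by a single echocardiographer who is not blinded. The subset could therefore be drawn with arm and results known.

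If the phrase is ignored, patients with intact AV conduction, who may pace little, are pooled with patients paced most of the time. An effect that needs three months of pacing to develop cannot show fully in the first group. In a trial of 26 patients, a chance imbalance in AV block between arms could also shift the echo and QRS comparisons.

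**Working it through.** The plan states no figure for the echo objective. Its 20 patients (26 enrolled) refer to the capture threshold, so there is no number to reproduce here. The check is a comparison of the text followed by two short calculations.

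**1. Is there an analysis set?** Secondary Objectives: a phrase on pacing need at 3 months, undefined. Inclusion Criteria: no requirement for ventricular pacing need. Design: the secondary analysis is restated with no restriction. Follow-up: the 3-month echo is for the patient, with no burden criterion. Statistical Analysis: silent. Two different sets fit this text.

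**2. Which endpoints can low burden dilute?** Let A be the acute effect of site while pacing, C the effect that accumulates over 3 months of pacing, and f the share of patients who rarely pace. Because every patient is paced during the measurement, the average arm difference is about

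A + (1 − f) × C, against A + C if all were paced throughout.

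- For a purely acute measure, C = 0 and the ratio is 1: no dilution. QRS duration, stroke volume and time to peak velocity, taken as acute paced measures, are of this kind.
- For a purely cumulative effect, A = 0 and the ratio is 1 − f.
- EF change may contain both parts.

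The documents give none of f, A or C. Assuming f = 0.25, the ratio lies between 0.75 (all cumulative) and 1 (all acute); with A = C it is 0.5 + 0.75 × 0.5 = 0.875. Assuming f = 0.5, it lies between 0.5 and 1; with A = C it is 0.75. The spread is too wide to support one figure.

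**3. How likely is imbalance in AV block?** The Randomization section gives 1:1 assignment with 26 envelopes and no stratification by indication. Assume arms of 13 and 13, and K patients with AV block (K is not in the documents). The number X in one arm is hypergeometric, the difference between arms is 2X − K, and C(26,13) = 10,400,600.

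- K = 13: a difference below 3 means X = 6 or 7. Probability = 2 × C(13,6) × C(13,7) / 10,400,600 = 2 × 1,716 × 1,716 / 10,400,600 = 0.566. So P(difference of 3 or more) = 0.434.
- K = 12: differences are even, so a difference below 3 means X = 5, 6 or 7. Probability = (2 × 792 × 3,003 + 924 × 3,432) / 10,400,600 = (4,756,752 + 3,171,168) / 10,400,600 = 0.762. So P(difference of 3 or more) = 0.238.
- K = 14: the same as K = 12 by symmetry.

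The range is about 0.24 to 0.43. The value at K = 13 is the higher because an odd count rules out exact balance.

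**The case against.** The strongest reply is that the sentence is only loosely written. The mention of 3 months may give the time of the comparison, which these endpoints get nowhere else in the objectives, and the words on requiring pacing may simply describe a pacemaker population. The unrestricted restatement under Design supports this. On that reading nothing is selected after randomisation. This stands as a possible reading, and a reader who infers that the plan definitely selects on pacing need goes further than the text. It does not remove the point: the sentence supports two analysis sets, and the plan does not say which applies.

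A second reply is that everyone is paced at the 3-month measurement. That is right, and it limits the point. A reader might infer that all the echo endpoints are diluted and might calculate a loss of power by scaling the whole effect by 1 − f. The documents do not support this: it would assume no acute effect at all, and neither the share who rarely pace nor any expected echo effect is given.

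Third, the documents offer no evidence that site or programming changes who needs pacing. That is fair, so the bias from selection is a possibility and not a demonstrated effect.

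Fourth, a covariate cannot be added to the paired tests now listed. That also stands, and the fix has to name a model.

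**Conclusion.** The point holds in a limited form. The echo objective can be read as restricting the comparison to a subset fixed after randomisation, eligibility is wider than that subset, and no section defines the echo analysis set. No restriction is needed for the acute paced measures. Dilution from low burden can reach only effects that build up over 3 months, mainly EF change, and its size cannot be computed from the documents.

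The imbalance probability of about 0.24 to 0.43 rests on assumed arms of 13 and 13 and on 12 to 14 patients with AV block. It shows that adjustment is worth planning; it does not show that an imbalance will occur. The endpoints concerned are secondary, and the primary threshold comparison is not affected. The text should still be settled before data are seen, given the open-label design and the non-blinded reader.

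**What to change.** In Secondary Objectives, replace the phrase on pacing need with a statement that the 3-month EF, stroke volume, dyssynchrony and QRS comparisons include all randomised patients with a 3-month assessment, analysed by randomised arm. State that no analysis set is defined by pacing need or burden at 3 months.

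In Statistical Analysis, specify a between-arm linear model for these endpoints with randomised arm and baseline AV block (yes or no) as terms. AV block comes from the pacing indication already collected; a patient with AV block among several indications counts as yes. Name the AV block subgroup, defined at baseline, as a supportive analysis for sustained-pacing effects. Report pacing burden by arm descriptively.

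The cost is a sentence or two in the objectives, a short new between-arm paragraph in the analysis section (which has none now), and one degree of freedom for the covariate in a small sample. No new data are needed and clinical management does not change.
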